### 16.3 Approach

#### 16.3.1 Sample collection and assessment of the clinical phenotype

For this sub-study, plasma samples from the SaDAPT trial and the ART initiation cohort collected at study sites in Lesotho will be used. For the assessment of the clinical phenotype (i.e. CD4 cell count, VL, occurrence of active TB or IRIS), the data collected during the SaDAPT trial and the ART initiation cohort as described above will be used. No clinical data or samples other than outlined in the protocol sections of the SaDAPT trial and the ART initiation cohort will be collected for this sub-study.

### 16.3.2 Measurement of the proteome

Proteome analysis will be conducted at the Department for Infectious Diseases and Hospital Epidemiology of the University Hospital Zurich in Switzerland under the supervision of [name]. Before shipment of the plasma samples to Switzerland, a specific Material Transfer Agreement will be submitted to NH-REC for review.

At the Department for Infectious Diseases and Hospital Epidemiology laboratory, plasma samples will be processed using the PreOmics iST kit in a 96 well format. Quantitative data will be acquired in diaPASEF mode (data independent acquisition – parallel accumulation serial fragmentation) on a timsTOF Pro mass spectrometer equipped with nanoElute chromatography system (Bruker). This method uses trapped ion mobility separations to increase sensitivity and resolving power combined with data independent acquisition to ensure robustness and data completeness. Preliminary data from serum samples shows we can robustly quantify 350-400 serum proteins from two microliters of human serum at a throughput of 50 samples per day making this compatible with analysis of large-scale cohorts. Importantly, only proteome analysis and no human genome analyses will be conducted.

### 16.3.3 Deconvolution of proteomic maps using computational biology

This study requires deconvolution of high dimensional data (the proteome) into a clinically meaningful predictor. We will use advanced statistical methods to deconvolute the high dimensional data. Specifically, we will primarily focus on the development of a proteome based voting score, given our publishing record and our experience with the diagnostic score development based on the published pairwise support vector machine (SVM) parameters and the robustness of the approach. However, we will also employ random forest models and deep neuronal network approaches and compare the diagnostic accuracy of different techniques.

We will follow a training – test cohort strategy whereby approximately 2/3 of all samples will be used as input into the machine learning algorithms. The remaining 1/3 of samples will be used as test set to evaluate the performance of the training set. Sample allocation to test and training sets is randomized. For external validation, we will test our proteome signature against already published proteome signatures in patients with active TB and HIV infection.

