### 2.3 ART initiation in PLHIV with presumptive TB

WHO recommends a four-symptom screening approach including cough, fever, night sweat and weight loss for clinical routine TB-screening among PLHIV. PLHIV presenting with at least one of the four symptoms are defined as having presumptive TB, and should subsequently undergo microbiological TB investigations to refute or confirm the diagnosis of active TB. Routine TB investigations typically consist of providing the patient two or three sputum bottles with the instruction to return with filled bottles the next day. If the patient returns with the sputum bottles, the samples are sent for analysis using nucleic acid amplification tests (Xpert MTB/RIF (Ultra)). The prevalence of presumptive TB among PLHIV not

taking ART has been estimated at 71% in a systematic review with considerable variation between studies. Studies in Kenya and South Africa have shown that the subsequent bacteriological work-up confirmed the presence of active TB in only 5%-19% of presumptive TB cases.

Until the release of a guideline update in 2021, WHO had recommended to delay initiation of ART in case of presumptive TB until TB has been investigated and TB treatment initiated if found TB-positive in order to reduce the risk of IRIS. This recommendation to defer ART for everyone with presumptive TB impairs access to same-day ART initiation for a large share of PLHIV. Whereas from a medical perspective delaying ART by a few days until a TB workup has been completed is reasonable, it may cause harm in resource-limited settings where delays between HIV diagnosis and ART initiation are associated with attrition from care, pre-treatment mortality and substantial out-of-pocket costs for patients, especially in remote areas where walking distances or transport costs to clinics are high. In these settings, offering same-day ART to PLHIV with presumptive TB while TB work-up is done in parallel may be a valuable strategy to engage and retain more patients in care and thus improve overall clinical outcomes.

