### 16.2 Objectives

- To diagnose active TB in PLHIV presenting with clinical symptoms
- To predict IRIS in PLHIV undergoing antiretroviral treatment
- To explore factors associated with control or progress of both TB and HIV infections

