### **Secondary outcomes analysis**

All secondary binary outcomes will be estimated as with the primary outcome and summarized with risk differences, risk ratios and 95% confidence intervals.

The secondary outcome of HIV viral suppression at different thresholds will be analyzed similar to the primary outcome - as a non-inferiority comparison followed by superiority if non-inferiority is established but no sensitivity analyses or effect modification will be done.

The secondary endpoints of retention in care, engagement in care, disengagement from care, lost to follow-up, and ART initiation within 7 or 28 days after enrollment will be assessed for superiority in the ITT population.

Non-traumatic mortality, hospitalizations, SAEs, AESIs and incidence of TB will be summarized descriptively as events are expected to be rare.

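### Protocol 16.3.3 tests its IRIS predictor on a random third of the samples, which may hold only a few IRIS cases; resampling by participant, stratified by outcome, would use them better

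*Protocol*

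**What the plan says.** The sub-study in Protocol section 16 uses stored plasma from the trial and the ART initiation cohort at the Lesotho sites. One of its three objectives (16.2) is "To predict IRIS in PLHIV undergoing antiretroviral treatment". Section 16.3.2 expects 350 to 400 measurable proteins per sample.

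Section 16.3.3 makes a voting score the main technique, adds random forests and neural networks, and will "compare the diagnostic accuracy of different techniques". On internal validation it says that "approximately 2/3 of all samples will be used as input into the machine learning algorithms", that "The remaining 1/3 of samples will be used as test set to evaluate the performance of the training set", and that "Sample allocation to test and training sets is randomized". The step it presents as validation outside its own data reads: "we will test our proteome signature against already published proteome signatures in patients with active TB and HIV infection".

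The section does not mention stratification by outcome, repeated splitting, cross-validation, allocation by participant, an expected number of IRIS cases or a minimum number.

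Protocol 7.1.1 defines the adverse event of special interest (AESI) as an event consistent with TB-IRIS. On its frequency, SAP 6.2 says "AESIs and incidence of TB will be summarized descriptively as events are expected to be rare"; Protocol 9.2.2 says the same.

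**The concern.** The plan regards IRIS as too rare for a formal comparison between arms over both countries. It nevertheless proposes to build and test an IRIS predictor from several hundred proteins in one country's samples, and gives no case count. Holding out a third costs twice: those cases are lost to model fitting, and the test set may then contain too few for a usable estimate of sensitivity. If the split is not stratified by outcome, the number of test cases is itself left to chance.

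Three further features add to this.

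- The split is described in terms of samples, while trial participants give plasma at enrolment and again at week 26 (Protocol 6.3 and 6.9). Unless allocation is by participant, one person can contribute to both sets.
- Several techniques are to be compared on accuracy, and no data are named for choosing between them.
- The step called external validation concerns active TB and HIV infection. It does not mention IRIS and, as worded, compares signatures; it does not apply a locked signature to new patients.

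At stake is whether an accuracy figure for IRIS from this sub-study could be relied on. Sections 16.1 and 16.4.1 look ahead to a point-of-care test.

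**Working it through.** The documents give no IRIS risk, expected count or sub-study size, so there is no figure of the plan's own to reproduce on this point.

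**Inputs from the documents**

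- Trial size 590 (Synopsis).
- Cohort size 1,300 to 1,800, trial participants included (Protocol 15.4.1 and 15.4.2).
- Seven of 11 sites are in Lesotho (Synopsis).
- Test share 1/3 (16.3.3).
- Adverse events in the cohort are recorded as in the trial (15.6), so cohort cases count.
- TB yield: earlier work-up "confirmed the presence of active TB in only 5%-19% of presumptive TB cases" (2.3).

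**Assumptions**

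- Lesotho share 50% to 64% (7/11 = 64%).
- IRIS risk per participant 0.5% to 2%, with 5% as a high case.

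**Step 1: Lesotho participants.** Trial plus cohort: 1,300 × 0.50 = 650, up to 1,800 × 7/11 = 1,145. Trial only: 590 × 0.50 = 295, up to 590 × 7/11 = 375.

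**Step 2: expected IRIS cases in the test third** = participants × risk × 1/3. For example, 650 × 0.01 / 3 = 2.2 and 1,145 × 0.01 / 3 = 3.8.

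| Assumed IRIS risk | Trial and cohort (650 to 1,145) | Trial only (295 to 375) |
|---|---|---|
| 0.5% | 1.1 to 1.9 | 0.5 to 0.6 |
| 1% | 2.2 to 3.8 | 1.0 to 1.3 |
| 2% | 4.3 to 7.6 | 2.0 to 2.5 |
| 5% | 11 to 19 | 4.9 to 6.3 |

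A second route starts from the TB yield in Lesotho trial participants, with an assumed 5% to 30% IRIS risk among TB cases. It gives 295 × 0.05 × 0.05 / 3 = 0.25 up to 375 × 0.19 × 0.30 / 3 = 7.1 test cases.

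**Step 3: precision.** If all k test cases are detected, the exact lower 95% limit for sensitivity is 0.025^(1/k):

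- k = 1: 2.5%
- k = 2: 16%
- k = 4: 40%
- k = 5: 48%
- k = 10: 69%

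These are best cases; any missed case lowers the limit.

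**Step 4: chance of an empty test set.** With T cases in all and a purely random split, P(none in the test third) is about (2/3)^T:

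- T = 3: 0.30
- T = 6: 0.09
- T = 10: 0.02

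With T = 5, the chance of at most one test case is (2/3)^5 + 5 × (1/3) × (2/3)^4 = 0.13 + 0.33 = 0.46.

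**Step 5: what resampling could gain.** With 3 to 6 cases in all, the test third holds about 1 to 2, with best-case lower limits of 2.5% to 16%. If every case is tested once in outer folds, the corresponding limits are 0.025^(1/3) = 29% to 0.025^(1/6) = 54%. This treats out-of-fold predictions as independent, so it is only a rough guide.

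**Step 6: the TB objective.** At the quoted yield, Lesotho trial participants alone give 295 × 0.05 = 15 up to 375 × 0.19 = 71 TB cases. About 5 to 24 of these would be in the test third.

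**The case against.** The strongest reply is that the case count is unknown and may be higher. The cohort enlarges the pool two- to fourfold over the trial's Lesotho participants. The quoted TB yield is bacteriological only, whereas this trial also counts clinical and radiological diagnoses (SAP 6.1). Unmasking IRIS can also arise from TB missed at enrolment (Protocol 7.1.3). All this stands, and it is why the result must be a range. A reader might infer that the test set will hold one or two IRIS cases; the documents do not support that. Over the Lesotho cohort, that count needs an IRIS risk of roughly 0.3% to 0.9%, and no risk is stated. Against a high count, AESIs are not asked about at week 26 or during tracing (Protocol 7.1.4), and a 5% risk across a cohort that includes people without TB symptoms sits uneasily with the expectation that events are rare.

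It can also be said that much is read from silence. Section 16.3.3 says only that allocation is randomized; stratification, or tuning within the training set, is not excluded. SAP 6.4 leaves sub-study analyses to another document. That is fair, but the deferral does not withdraw the split that the protocol states, and section 16.3.3 is where a safeguard would be expected.

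A reader might further infer that the best of the three techniques will be picked on the test set, which would make its accuracy optimistic. The protocol does not say so: the voting score is already the primary focus. The risk exists only because no data are named for any such choice.

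Finally, resampling adds no cases, and with 3 to 5 cases nested folds would also be unstable. This stands and limits what the change can achieve.

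**Conclusion.** The point holds for the IRIS model. The protocol evaluates it on a random 2/3 v 1/3 split of samples, with no stratification or resampling described, for an outcome that the plan expects to be rare. Under the assumed Lesotho share and the full cohort, the test third would hold about 1 to 2 cases at 0.5% risk, 2 to 4 at 1% and 4 to 8 at 2%, and fewer if only trial participants contribute. Over most of that range, even perfect detection leaves the lower limit for sensitivity below 50%.

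A reader might conclude that the IRIS objective cannot be answered. That goes too far: it would apply only at the low end of the assumptions, and at 5% risk the test third would hold 11 to 19 cases. The criticism does not extend to the TB objective, and it does not affect the trial's own endpoints. The remark on external validation holds on the wording alone and needs no assumption about case numbers.

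**What to change.** In Protocol 16.3.3, or in the sub-study's own analysis plan:

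- For the IRIS model, replace the split by repeated cross-validation over participants, stratified by outcome. Keep each person's enrolment and week-26 samples in the same fold, and confine tuning and any choice between techniques to inner folds. If a hold-out is kept, at least stratify it by outcome and allocate by participant.
- Keep the voting score as the one primary technique and report the others as secondary.
- State the expected number of IRIS cases as a range. Report the IRIS model as exploratory, with confidence intervals, if cases are few. The documents offer no basis for a particular cut-off, so the authors should set and justify one before the samples are analysed.
- Call the comparison with published signatures benchmarking, since as worded it does not validate the IRIS signature in new patients.

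The cost is a wording change, computing time and a validation that is less simple to describe. No new samples are needed. If IRIS proves very rare, the estimates will remain imprecise whichever scheme is used.

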### 6.3 Baseline assessment (study staff)

Enrolment will take place in an environment as private as possible, within the constraints of the clinic setting, so that confidentiality can be assured.

On enrolment, the following procedures will be performed:

- Brief clinical history and physical examination including:
  - o HIV, ART, TB and general clinical history
  - o Sociodemographic characteristics, health status, possible comorbidities and co-medications
  - o Measurement of height and weight with determination of BMI and vital signs
- CD4 cell count
- TB investigations
  - o According to local routine practices using Xpert MTB/RIF (Ultra), clinical assessment and chest x-ray if available
  - o If a urine lipoarabinomannan (LAM) test or any other additional examinations are performed by the responsible routine clinic staff as part of standard of care, the results will be registered by study staff. No LAM assays will be provided by the study team.
- Collection of two tubes of venous blood for centrifugation and storage and subsequent HIV genotyping and resistance testing or other related research. If venous blood draw is not possible, a dried blood spot (DBS) will be collected.

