### **6.9 Study visit, week 26 (week 22 - 30) (routine staff and study staff)**

The study visit will be scheduled together with the routine 6 month ART refill visit. Study staff will ensure that a VL gets measured for the assessment of the study endpoint. In addition to adherence counseling and ART refill by routine staff, study staff will take a targeted clinical history including inquiry about ART and TB status, current health status, medication, adherence and possible SAEs since enrollment. Collection of two tubes of venous blood for centrifugation and storage (or a DBS if venous blood draw is not possible) and subsequent HIV genotyping and resistance testing or other related research (as specified in section 16)

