### 15.5.4 Follow-up

HIV care will be provided by routine clinic staff, according to national guidelines with no intervening of study staff.

Study staff will document date of ART initiation, dates and results of possible TB investigations, dates of ART refills, dates and results of VLs and information about possible relevant complications based on data recorded by routine staff in the respective clinical registries. As for the SaDAPT trial, there will be register reviews 28 days and 30 weeks after enrolment to ensure complete and correct data collection. At the time of the 6-months routine VL measurement (window 22-30 weeks after enrolment), the same clinical assessment will be performed as for the SaDAPT trial participants and plasma samples (or DBS if blood draw not possible) will be collected at the study sites in Lesotho. At the study sites in Malawi in participants without a documented VL between 22 and 30 weeks after enrolment, a DBS might be collected (collection of plasma samples is not possible due to resource constraints). A subsample of ART initiation cohort participants without documented VL results will be traced back via phone calls and home visits to ascertain their outcome.

One year (56 weeks) and two years (112 weeks) after enrolment, register reviews will be conducted to assess the number of participants retained in care, the rate of viral suppression and the occurrence of SAEs and AESIs up to the respective time points. Again, a subsample of participants without documented VL result one and two years after enrolment will be traced back, if resources allow. In Lesotho plasma samples may be collected one and two years after enrolment if resources allow.

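### The proteome sub-study randomises samples to training and test sets although one participant may give several samples, so as written the test set is not independent

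*Protocol*

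**What the plan says.** Protocol 16.3.3 counts both sets in samples. For training, "approximately 2/3 of all samples will be used as input into the machine learning algorithms". For testing, "The remaining 1/3 of samples will be used as test set to evaluate the performance of the training set". It then adds that "Sample allocation to test and training sets is randomized". The section does not name the participant as the unit, does not say how repeat samples are kept together, and does not restrict a model to one time point.

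Protocol 16.3.1 defines the input: "plasma samples from the SaDAPT trial and the ART initiation cohort collected at study sites in Lesotho will be used". Enrolment samples are not singled out. Repeat samples are planned elsewhere in the protocol:

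- Trial participants give venous blood at enrolment (6.3) and again at week 26 (6.9). The week-26 sentence points to the proteome section: "subsequent HIV genotyping and resistance testing or other related research (as specified in section 16".
- Cohort members in Lesotho give plasma at enrolment (15.5.2) and at weeks 22 to 30 (15.5.4).
- Later draws are possible: "In Lesotho plasma samples may be collected one and two years after enrolment if resources allow" (15.5.4). Trial participants also belong to the cohort (15.4.1).

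SAP 6.4 leaves sub-study analyses to another document, so 16.3.3 is the only split rule available here.

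**The concern.** A test set estimates accuracy in new people only if the people in it are new to the model. If one person's enrolment sample trains the classifier and the week-26 sample tests it, the two measurements share whatever is stable in that person's proteome. If they also share a label, the classifier can score well by recognising individuals. With 350 to 400 proteins per sample (16.3.2), and random forests and deep networks also planned, a model has room to do this.

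The held-out third is the only internal accuracy estimate that the sub-study describes. Section 16.3.3 also plans to compare techniques on diagnostic accuracy, and an overlap could favour the technique that best memorises people. The external validation step compares the signature with published signatures and names no independent participants, so it would not clearly expose the problem.

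**Working it through.** The sub-study states no sample size or accuracy figure, so there is no figure of the plan's own to reproduce.

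**Step 1: overlap under the split as written.** The inputs are the training share of 2/3 (16.3.3) and k plasma samples per person. From 6.3, 6.9, 15.5.2 and 15.5.4, k = 2 is planned and k = 3 or 4 is possible. Treating each sample as allocated independently:

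- Share of people with samples in both sets = 1 − (2/3)^k − (1/3)^k
- Share of test samples with a same-person sample in training = 1 − (1/3)^(k−1)

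| k | People in both sets | Test samples with a same-person training sample |
|---|---|---|
| 1 | 0% | 0% |
| 2 | 1 − 4/9 − 1/9 = 44% | 1 − 1/3 = 67% |
| 3 | 1 − 8/27 − 1/27 = 67% | 1 − 1/9 = 89% |
| 4 | 1 − 16/81 − 1/81 = 79% | 1 − 1/27 = 96% |

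Fixing the training share at exactly two thirds barely changes this. For 300 people with two samples each, the share in both sets is 2 × (2/3) × (200/599) = 44.5%. If whole participants are allocated, it is 0% for any k.

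**Step 2: what the overlap can do to accuracy.** This needs inputs that the documents do not give, so they are assumed: 300 people, 375 proteins (the middle of the stated range), no true signal, a label held constant per person, a linear kernel ridge classifier and 60 replicates per setting. The correct AUC is 0.50. Mean test AUC:

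| Samples per person | Case share | Within-person correlation | Split by sample | Split by participant |
|---|---|---|---|---|
| 2 | 10% | 0 / 0.2 / 0.5 / 0.8 | 0.501 / 0.605 / 0.754 / 0.829 | 0.484 / 0.505 / 0.505 / 0.501 |
| 2 | 20% | 0 / 0.2 / 0.5 / 0.8 | 0.509 / 0.562 / 0.704 / 0.795 | 0.490 / 0.494 / 0.513 / 0.498 |
| 4 | 10% | 0 / 0.2 / 0.5 / 0.8 | 0.497 / 0.690 / 0.879 / 0.968 | 0.496 / 0.510 / 0.492 / 0.506 |
| 4 | 20% | 0 / 0.2 / 0.5 / 0.8 | 0.503 / 0.644 / 0.818 / 0.946 | 0.500 / 0.507 / 0.503 / 0.500 |

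**Step 3: how much depends on the label and the time point.** The same kind of null simulation was run with 15% cases, two samples per person and a split by sample, at within-person correlation 0.2 / 0.4 / 0.6:

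- Label constant per person: AUC 0.59 / 0.66 / 0.76. Other runs under these assumptions gave 0.57 to 0.59, 0.61 to 0.68, and 0.71 to 0.76.
- Label tied to the visit, all week-26 samples negative: 0.52 / 0.50 / 0.47. A further run gave about 0.47 to 0.48.
- Enrolment samples only: 0.47 / 0.50 / 0.49.

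So the overlap in Step 1 follows from the text. The inflation in Step 2 needs two further conditions: repeat samples in the same model, and a label shared across a person's samples.

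**The case against.** The strongest reply is that the two predictive objectives in 16.2 point to enrolment samples. Diagnosing TB concerns people presenting with symptoms, and the trial defines prevalent TB by work-up begun at enrolment and completed within 28 days (4.1.3). Both IRIS definitions in 7.1.3 place onset within three months of starting ART, so for someone who starts near enrolment a week-26 sample comes too late to predict it. With one enrolment sample per person, sample and participant are the same unit and no overlap arises. TB status can also change between visits, because a TB diagnosis is expected to lead to treatment (6.6.1), so a shared label is not a given. Some draws will yield a dried blood spot instead of plasma, so not everyone will have two plasma samples. The analysis detail may sit in a document not seen here.

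Much of this stands as a limit on size. A reader might infer that the protocol has decided against splitting by participant, or that the reported accuracy will be too high. The documents support neither. They never contrast the two units, and they do not say how repeat samples are labelled or which samples enter which model. Nor do they show a fault in feature selection or tuning, since 16.3.3 already feeds only the training share to the algorithms.

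The reply does not remove the point. No restriction to enrolment samples is written down, 6.9 links the week-26 draw to section 16, and the third objective (factors associated with control or progress of TB and HIV) fits later samples. The rule that is written allocates samples.

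**Conclusion.** The concern holds in a limited form. Under the stated rule, with all Lesotho plasma eligible, 44% of people with two samples, 67% with three and 79% with four would be expected in both sets. The test set would then not be independent. These shares rest only on the 2/3 fraction and the number of samples per person.

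Inflated accuracy is conditional. If repeat samples enter one model with a person-level label, the illustrative null AUC with two samples per person is about 0.56 to 0.76 for an assumed within-person correlation of 0.2 to 0.6, against about 0.50 when split by participant. If labels are visit-specific, or only enrolment samples are used, there is little or no inflation. The AUC values show the mechanism; they do not forecast this study's bias. The point concerns the accuracy estimate of a laboratory sub-study and leaves the trial's primary analysis untouched.

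**What to change.** In Protocol 16.3.3, replace the sentence on random allocation with one of these:

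- Participants, identified by participant number, are randomly allocated 2:1 to the training and test sets, and all samples of a participant stay in the same set.
- Each model uses one pre-specified sample per participant, with the time point named for each objective.

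Either option removes the overlap however repeat samples are labelled. The first keeps all the data; the second uses fewer samples per model. Samples already carry the participant number (16.4.1), so no new data or laboratory work is needed. The cost is one sentence, repeated in the separate sub-study analysis plan if there is one.
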